12.4 Protocol Deviations

A deviation is any instance(s) of failure to follow, intentionally or unintentionally, the requirements of the protocol. It is expected that the Investigator will conduct this clinical trial in compliance with the protocol and all applicable regulations governing the conduct of clinical research involving human subjects. Failure to do so could result in one or all of the following:

- observation in the monitoring report
- deviation to document the event
- corrective action plan

- site disqualification
- notification to the regulatory authorities depending on the severity of the deviation

The investigator is responsible for protecting the safety and welfare of the clinical research subjects.

Compliance with Protocol:

The Investigator or person designated by the investigator will document and explain any deviation from the approved protocol that occurs during the course of the clinical trial. The date and reason for each deviation will be documented. (CFR 21 812.140 Records)

The investigator should not implement any deviation from, or changes of, the protocol without agreement by the sponsor and prior review and documented approval/favorable opinion from the IRB/IEC of an amendment, except where necessary to eliminate an immediate hazard(s) to trial subjects, or when the change(s) involves only logistical or administrative aspects of the trial (e.g., change of monitor(s), change of telephone number(s)).

The investigator may implement a deviation from, or a change in, the protocol to eliminate an immediate hazard(s) to trial subjects without prior IRB/IEC approval/favorable opinion. As soon as possible, the implemented deviation or change, the reasons for it, and, if appropriate, the proposed protocol amendment(s) should be submitted:

- (a) To the IRB/IEC for review and approval/favorable opinion;
- (b) To the sponsor for agreement and, if required;
- (c) To the regulatory authority(ies).

21 CFR 812.150 (4) states "...except in such an emergency, prior approval by the sponsor is required for changes in or deviations from a plan, and if these changes or deviations may affect the scientific soundness of the plan or the rights, safety, or welfare of human subjects, FDA and IRB in accordance with 21 CFR 812.35(a) also is required".

Emergency deviations must be reported to the sponsor and IRB within 5 days. The following examples are deviations that could impact subject safety, affect the integrity of study data and/or affect subject's willingness to participate in the study. These deviations are significant and require immediate sponsor notification upon investigator awareness:

- Failure to obtain informed consent, i.e., there is no documentation of informed consent
- Informed consent obtained after initiation of study procedures
- Enrollment of a subject who did not meet all inclusion/exclusion criteria
- Performing study procedure not approved by the IRB
- Failure to report serious adverse event to the IRB and sponsor
- Investigational study device dispensed without obtaining informed consent

13. Device Complaints and Troubleshooting

The Medtronic 24 Hour Help Line (HL) or appropriate investigational center staff will be consulted for device troubleshooting (e.g. assistance is needed by subject to operate their device(s)). If subject/parent/caregivers call the HL, they are instructed to notify the HL operator that they are currently participating in a clinical research study. All device complaints that are reported to the HL will be documented by the HL staff.

The investigational center will be provided with a copy of all HL calls for their subjects. The HL calls should be reviewed for investigational center staff awareness for the possibility of an AE. If an AE is detected the investigational center staff will also complete an AE eCRF.

All device deficiencies reported directly to the investigational center staff by a subject should either be reported to the HL by the subject or investigational center staff. A device deficiency is any communication that alleges inadequacy of a medical device with respect to its identity, quality, durability, reliability, safety, or performance. NOTE: Device deficiencies include malfunctions, use errors, and inadequate labeling.

All Device returns will follow the 24 HL procedures. To return a study device as part of a complaint the investigational center and or subject are to call the 24 HL.

Descriptive discussion of device performance issues and complaints will be performed.

It is the responsibility of the Investigator to abide by the device malfunction & complaint reporting requirements stipulated by the reviewing IRB and the sponsor.

14. Safety

14.1 Potential Risks

14.1.1 Potential side effects related to insulin pump infusion set may include

- Infection
- Skin irritation/ Redness
- Bruising
- Discomfort/ Pain
- Bleeding
- Irritation
- Rash

Investigational Centers and subjects/parents/caregivers will be instructed to follow the provided user guides for insertions and care of infusion sets. If an infusion site becomes irritated or inflamed, the infusion set should be removed and another placed in a new location.

14.1.2 Potential risks with insulin administration and pump use

Due to the use of insulin, there is a potential for adverse events related to the infusion of insulin and the potential interruptions of insulin delivery. These risks all may include:

- Hypoglycemia
- Diabetic Ketoacidosis (DKA)
- Hyperglycemia
- Severe Hypoglycemia with or without associated seizure, coma or death.

14.1.3 Potential risks with sensor use

Potential risks include the following:

- Skin Irritation or reaction to adhesives
- Bruising
- Discomfort
- Redness
- Bleeding
- Pain
- Rash
- Infection
- Irritation from tapes used with glucose-sensing products

- Raised Bump
- Appearance of a small "freckle-like" dot where needle was inserted
- Allergic reaction
- Syncopal episode secondary to needle insertion
- Soreness or tenderness
- Swelling at insertion site
- Sensor fracture, breakage or damage
- Minimal blood splatter associated with sensor needle removal

14.1.4 Potential adverse events with serter use:

- Skin infection around area where serter is used

14.1.5 Potential risks specific to TS Feature:

- When TS is turned ON, the feature may not activate when the blood sugar is low.
- When TS is turned ON, the feature may falsely activate when the subject's blood sugar is not low.
- The TS feature is not intended to prevent or treat hypoglycemia.

14.1.6 Potential risks related to frequent finger stick testing

- Potential risks associated with frequent meter testing of blood glucose and ketones include discomfort and bruising at tips of fingers.

14.1.7 Potential risks related to venous blood sampling

- Potential risks associated with drawing blood include discomfort and bruising.
- Syncopal episode can occur secondary to needle insertion.

14.1.8 Potential risks and mitigations for pediatric subject population

The pediatric subject population has an increased risk for hypoglycemia, including severe hypoglycemia.

Standard mitigations in pediatric subjects include:

- Training of primary caregivers will be conducted in addition to subject training.
- Subject instruction to test BG via finger stick testing 4-6 times a day.
- Subject instruction to adhere to 100% sensor wear.
- Subject instruction to use the bolus wizard when determining meal or correction bolus.

14.2 Reporting of Adverse Events

The Medtronic Clinical Research Department, in conjunction with the Medtronic Regulatory Affairs Department, in Northridge, California will monitor and manage adverse event reporting for the study.

A complete description of the event including treatment and interventions provided by medical professionals will be included on the AE eCRF. It is expected that the investigator will provide the sponsor with the necessary medical records to support the adverse event.

Throughout the course of the study, Investigational Center staff will make all efforts to remain alert to possible reportable adverse events or untoward findings. Reports of adverse events will be requested from subjects/parents/caregivers at each visit and adverse event eCRFs will be completed as required. Investigational Center staff will assess the intensity of each adverse event and its relationship to study procedures or devices.

Adverse events that are assessed to have a relationship to a study procedure or study device will be analyzed by the Human Factors group at Medtronic Diabetes to determine whether or not there is a connection to mis-use of the device(s) or user error.

Events that are moderate and severe in intensity, all SAE, SADE and UADE that have not resolved at the time of the subject's discontinuation or completion of the study will be followed until the medical outcome is determined or until no further change in the condition is expected. All adverse events that have not resolved will have a final status of 'ongoing'.

Adverse Events reported to sponsor:

The Investigator or designee will report all adverse events to the sponsor:

- Adverse Events not related to the study device or study procedure
- Adverse Events related to the study device
- Adverse Events related to study procedures
- UADE (Unanticipated Adverse Device Effect)
- All SAE (Serious Adverse Events)
- Severe Hypoglycemia
- DKA (Diabetic Ketoacidosis)

A pre-existing medical condition will only be documented as an adverse event if the condition worsens during the course of the subject's participation in the study. Non-serious Adverse events should be entered on the appropriate Electronic Case Report Form (eCRF) within 14 days of subject report to the site. For serious adverse events, reporting is required to sponsor within 24 hours of site awareness.

14.3 Review of Severe Hypoglycemia and DKA.

Severe hypoglycemia, and DKA will be adjudicated by the Clinical events committee (CEC) comprised of external physicians. The adjudication will include device relatedness and whether the event was considered to be serious or not. The CEC may use Carelink reports, medical records and information on CRF to make determination.

14.4 Definitions

Adverse Event (AE) (ISO14155: 2011)

Any untoward medical occurrence, unintended disease or injury, or untoward clinical signs (including abnormal laboratory findings) in subjects, users or other persons, whether or not related to the investigational medical device.

Note 1: This definition includes events related to the investigational medical device or the comparator.

Note 2: This definition includes events related to the procedures involved.

Note 3: For users or other persons, this definition is restricted to events related to investigational medical devices.

Adverse Device Effect (ADE) (ISO 14155: 2011)

Any untoward and unintended response to a medical device.

Note 1: This includes any adverse event resulting from insufficiencies or inadequacies in the instructions for use, the deployment, the implantation, the installation, the operation, or any malfunction of the medical device.

Note 2: This includes any event that is a result of a use error or intentional misuse.

Serious Adverse Event (SAE) (ISO 14155: 2011)

An adverse event that

(a) Led to a death

(b) Led to a serious deterioration in the health of the subject that

- resulted in life threatening illness or injury,
- resulted in a permanent impairment of a body structure or a body function
- required in-patient hospitalization* or prolongation of existing hospitalization
- resulted in medical or surgical intervention to prevent permanent impairment to a body structure or a body function

(c) Led to fetal distress, fetal death or a congenital abnormality or birth defect

**Inpatient Hospitalization is defined as: 24 hour acute admission to the hospital based on urgent medical need rather than elective admission.*

Note: A planned hospitalization for pre-existing condition, or a procedure required by the CIP, without a serious deterioration in health, is not considered to be a serious adverse event.

Serious Adverse Device Effect (SADE) (ISO 14155: 2011)

Adverse device effect that has resulted in any of the consequences characteristic of a serious adverse event.

Unanticipated Adverse Device Effect (UADE) (21 CFR 812.3(s))

Any serious adverse effect on health or safety or any life-threatening problem or death caused by, or associated with, a device, if that effect, problem, or death was not previously identified in nature, severity, or degree of incidence in the investigational plan or application (including a supplementary plan or application), or any other unanticipated serious problem associated with a device that relates to the rights, safety, or welfare of subjects.

Severe Hypoglycemia is an event requiring assistance of another person (due to altered consciousness) to actively administer carbohydrate, glucagon, or other resuscitative actions.

This means that the subject was impaired cognitively to the point that he/she was unable to treat his or her self, was unable to verbalize his or her needs, and was incoherent, disoriented and/or combative.

These episodes may be associated with sufficient neuroglycopenia to induce seizure or coma. Plasma glucose measurements may not be available during such an event, but neurological recovery attributable to the restoration of plasma glucose to normal is considered sufficient evidence that the event was induced by a low plasma glucose concentration. (**adapted from the American Diabetes Association Workgroup on Hypoglycemia, 2005**)

“Severe Hyperglycemia” is defined as Hyperglycemia (blood glucose >300 mg/dL) with blood glucose ketones >0.6mmol/L or accompanied by symptoms of nausea, vomiting or abdominal pain.

“Diabetic Ketoacidosis/DKA” is defined as: Hyperglycemia (blood glucose greater than 250 mg/dL or greater than 13.9 mmol/L) with either low serum bicarbonate (less than 15 mEq/L) and/or low pH (less than or equal to 7.24) Anion gap (greater than 12) and either ketonemia or ketonuria and requiring treatment within a health-care facility. (**American Diabetes Association-Diabetes Care, Volume 27, Supplement 1, January 2004**)

14.5 Device or Procedure Relatedness:

The relatedness of the event to the study device or procedures will be determined for each adverse event. Subjects participating in this study have type 1 diabetes and it is expected that due to the disease subjects will have adverse events that are part of their disease. It is expected that the investigator will assess all events to determine if the event was related to the disease or if the event was related to the device or study procedure. An adverse event is not automatically related to the study device or procedure simply because the subject is wearing the device and participating in the study. The event should be reviewed to determine if the device or study procedure could have possibly caused the event and therefore is related to the study device or procedure.

The investigator will review all elements surrounding the event to properly determine relatedness – this would include the subjects/parents/caregivers description of the event, study device downloads and medical records (if applicable) from the treating facility. These records will be made available to the

sponsor and the Clinical Events Committee at the request of the sponsor. The following definitions should be considered when determining the relationship of the event to the device or study procedure:

Definite – clearly related to the device or procedure

Probable – likely related to the device or procedure

Possible – may be related to the device or procedure

Unlikely – doubtfully related to the device or procedure

Not Related – clearly not related to the device or procedure

If the investigator determines the event meets the definition of definite, probable or possible the event should be considered related and the Yes box on the AE eCRF would be checked for the question related to. If the investigator determines the event meets the definition of unlikely, not related or unknown the event should be considered unrelated and the NO box would be checked on the AE eCRF for the question was the event related to.

14.6 Event Intensity (severity):

Mild: Transient, needing no special treatment, and/or does not interfere with the subject's daily activity.

Moderate: Low level of inconvenience or concern to the subject and may interfere with daily activities, but is usually improved by simple therapeutic remedy.

Severe*: Interrupts a subject's daily activity and typically requires intervening treatment.

Please Note*: The terms "serious" and "severe" are not synonymous. Severe is often used to describe the intensity (severity) of a specific event (as in mild, moderate, or severe myocardial infarction); the event itself, however, may be of relatively minor medical significance (such as severe headache). This is NOT the same as "serious" which is based on the definition of "serious criteria" which have been provided.

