6.4 Safety Analysis

All site reported adverse events for enrolled subjects will be summarized. The summary will include all adverse events and adverse events by: Insulin Pump Infusion set; Insulin administration and pump use; Sensor Use; Severe Hypoglycemia; Severe Hyperglycemia; Diabetic Ketoacidosis; Adverse Device Event; Serious Adverse Event and Unanticipated Adverse Device Effect. Adverse Events by Investigator will also be provided. No formal statistical analysis will be carried out.

In addition, data will be collected for a descriptive summary of device disposition; adverse events; device performance and user acceptance. Safety analysis will include a summary of the following:

All adverse events including

- Serious Adverse Events (SAE)
- Unanticipated Adverse Device Effects (UADE)
- Incidence of Severe (clinical) Hypoglycemia
- Incidence of Severe Hyperglycemia
- Incidence of Diabetic Ketoacidosis (DKA)

Adverse Events will be stratified by

- **Age**
 - Children age 7-12 years
 - Children age 13-15 years
- **Race**
 - American Indian/Alaska Native
 - Black/African-American
 - White - anticipated maximum 80%
 - Native Hawaiian/Other Pacific Islander
 - Asian
 - Subject Refused
- **Ethnicity**
 - Hispanic/Latino
 - Non-Hispanic/Non-Latino
 - Subject Refused
- **Diabetes cohorts based on BMI percentile:**

Weight Status Category	Percentile Range	N=Minimum
Underweight	Less than the 5th percentile	2
Healthy weight	5th percentile to less than the 85th percentile	30
Overweight	85th to less than the 95th percentile	4
Obese	Equal to or greater than the 95th percentile	2

BMI Percentiles according to CDC:

http://www.cdc.gov/healthyweight/assessing/bmi/childrens_bmi/about_childrens_bmi.html

[figure not shown]
- **Gender**
 - Male
 - Female
- **Hypoglycemic awareness at Baseline Questionnaire**
 - Patients with intact hypoglycemic awareness (95% confidence interval will be provided)
 - Patients who have impaired hypoglycemic awareness (95% confidence interval will be provided)
- Frequency and average duration of hypoglycemic event (based on two weeks prior to the adverse event)

- The one-sided 95% upper confidence limit of severe adverse event incidence rate (DKA and severe hypoglycemia) will be calculated. Individual one-sided 95% confidence limit for DKA only and severe hypoglycemia only will also be provided.

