Study Activities at Home between visits		
Upload the Pump every 21 days
 
Change Sensors as required
 
Test urine ketones daily and enter test results into CareLink Clinical
 
Call the study doctor and his staff if you are experiencing any medical problem either related to your diabetes or unrelated to your diabetes
 
Call the Medtronic 24 Hr helpline if you have a device problem
 
Fill out a Sensor Dislodgement Diary as needed
	
Upload the Pump every 21 days
 
Change Sensors as required
 
Test urine ketones daily and enter test results into CareLink Clinical
 
Call the study doctor and his staff if you are experiencing any medical problem either related to your diabetes or unrelated to your diabetes
 
Call the Medtronic 24 Hr helpline if you have a device problem
 
Fill out a Sensor Dislodgement Diary as needed
	
Upload the Pump every 21 days
 
Change Sensors as required
 
Test urine ketones daily and enter test results into CareLink Clinical
 
Call the study doctor and his staff if you are experiencing any medical problem either related to your diabetes or unrelated to your diabetes
 
Call the Medtronic 24 Hr helpline if you have a device problem
 
Fill out a Sensor Dislodgement Diary as needed
	

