- Instruct subject/parent/caregiver on the use of the Sensor dislodgement Diary
 - Subject/parent/caregiver will be instructed to record sensor dislodgement occurrences in the Sensor dislodgement Diary.
- Discuss glucose sensor wear requirement.
 - Glucose sensors should be worn throughout the course of the study
- Train subject/parent/caregiver on the use of CareLink Clinical which includes that this application should only be used to upload the study pump and not for data analysis or diabetes management.
- Instruct subject/parent/caregiver to use either Humalog or Novolog insulin

- Instruct subject/parent/caregiver to contact the Medtronic 24hr HelpLine in the event they experience problems with their study devices.
- Instruct subject/parent/caregiver to test for urine ketones daily and to record results in CareLink Clinical.
 - Urine ketone test strips will be provided by sponsor free of charge to subjects.
 - The urine ketone strips will not be tracked by sponsor.
- Instruct subject/parent/caregiver to report all adverse events as soon as possible. This would include any new medical problem or deterioration of an existing medical problem, such as sickness or glycemic problems. If necessary refer subject/parent/caregiver to the subject's own providers or an emergency facility for treatment.

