10.8 Study Closure

Upon completion of the study, when all subjects have completed their visit schedules, all eCRFs have been entered and all related queries have been resolved, Medtronic and/or its designees will notify the Investigational Center of its intention to close out the study and a close-out visit will be conducted. The Monitor will ensure that the Investigator's regulatory files are up-to-date and complete and that any outstanding issues from previous visits have been resolved. Other issues that will be reviewed at this visit include discussing retention of study files, possibility of Investigational Center audits, and notifying the IRB of study closure.

11. Devices and Supplies

Subjects will be given all study devices and supplies at each scheduled visit (except final study visit). Investigational sensors that are provided by the sponsor will be tracked from Sponsor to investigational center.

11.1 *Investigational Devices*

Investigational devices to be used in this study include:

- Minimed MM530G Pump (labeled as Medtronic MiniMed Paradigm® Insulin Pump, MMT-751); referred to as study pump in the protocol
- Medtronic CareLink® Therapy Management Software for Diabetes (MMT-7334) –referred to as CareLink Clinical in the protocol
- Medtronic MiniMed Enlite™ Glucose Sensor (MMT-7008); referred to as glucose sensor in the protocol
- Medtronic MiniMed MiniLink® 2 REAL-Time Transmitter (MMT-7713)
- Enlite™ Serter (MMT-7510)

11.2 *Non-Investigational Devices*

- Medtronic MiniMed charger (MMT-7705)
- Medtronic MiniMed CareLink® USB (MMT-7305)
- Test Plug (MMT-7706)
- Bayer CONTOUR™ Next Link Blood Glucose Meter.

11.3 *Non-Investigational Supplies*

- Urine Ketone sticks
- Infusion Sets
- IV3000 tape
- Lancet device
- Lancets
- Batteries for Meter
- Alcohol swabs
- AAA Energizer batteries

11.4 *Study Materials*

- User Guides for study devices
- Study instructions
- Subject Questionnaires

Study supplies must be securely stored during the study.

11.5 *Device Accountability*

Good clinical research practice requires that investigators and research teams ensure accurate accountability for any investigational device used in a research trial. It is expected that all investigational devices will be used in the manner intended during the study, that they will be stored under appropriately controlled conditions and that they will be used only by (on) subjects who have consented to participate in the research study.

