14.7 Clinical Events Committee

A clinical events committee consisting of external physicians with an expertise in Endocrinology and the management of Type 1 diabetes including CGM will be convened. The CEC will review all reports of:

- Diabetic Ketoacidosis
- Severe Hypoglycemia
- Serious Adverse Event
- Serious Adverse Device Effect
- Unanticipated Adverse Device Effect

The CEC will assess these events to determine agreement or disagreement with the investigator determination of the event. The investigator will be notified of any disagreement in assessment of an event by the CEC.

15. Administrative Considerations

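### The severe hyperglycemia endpoint has a ketone criterion in mmol/L, but every ketone test the protocol specifies by sample type is a urine test, so symptom-free events are under-identified

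*Protocol*

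**What the plan says.** The Protocol Synopsis, Protocol Section 6.4 ("Incidence of Severe Hyperglycemia") and SAP Section 3.1.6 all list severe hyperglycemia among the safety outcomes.

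Protocol Section 14.4 defines it as glucose above 300 mg/dL "with blood glucose ketones >0.6mmol/L or accompanied by symptoms of nausea, vomiting or abdominal pain". The printed phrase runs glucose and ketones together. The unit, mmol/L, shows that a concentration is meant.

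On ketone measurement, the protocol says:

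- Section 10.1, training instructions: "Instruct subject/parent/caregiver to test for urine ketones daily and to record results in CareLink Clinical". The sponsor supplies the urine strips and does not track them.
- Table 1, home activities between visits: "Test urine ketones daily and enter test results into CareLink Clinical".
- Section 11.3, supplies: the only ketone item is "Urine Ketone sticks".
- Section 14.1.6, finger-stick risks: a reference to "frequent meter testing of blood glucose and ketones".

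On review of events, Section 14.7 opens its list with "The CEC will review all reports of" and then names DKA, severe hypoglycemia, SAE, SADE and UADE. Severe hyperglycemia is not named there, nor in Section 14.3.

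**The concern.** The definition has two routes beyond the glucose threshold: a ketone value or symptoms. If the ketone route needs a measurement that the study does not specify, the endpoint in practice counts symptomatic events, plus any event for which someone outside the study measured blood ketones.

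This matters for a feature that stops insulin delivery. Section 14.1.2 names hyperglycemia and DKA among the risks of interrupted delivery, and Section 14.1.5 warns that the feature may activate when glucose is not low. The study has a single arm, so no comparator shares the under-ascertainment and the observed incidence stands alone. An incidence that misses symptom-free ketosis errs in the direction that favours the device.

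A second possibility is that sites substitute the urine result for the stated criterion. Each of up to 20 centers would then need its own conversion, and the incidence would mix definitions.

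**Working it through.** There is no planned severe hyperglycemia rate to reproduce, so this is a comparison of sections.

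**Step 1: what an event needs.** From Section 14.4, an event requires glucose above 300 mg/dL and either (a) ketones above 0.6 mmol/L or (b) one of the three listed symptoms. Without (b), only (a) can qualify it.

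**Step 2: what the study measures.**

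| Source | Ketone measurement |
|---|---|
| Protocol 10.1, training | Urine, daily, recorded in CareLink Clinical |
| Protocol Table 1, home activities | Urine, daily, recorded in CareLink Clinical |
| Protocol Table 1, Visits 2 to 4 | Urine strips distributed; also ketone strips with no sample type given |
| Protocol 11.3 | Urine sticks |
| Protocol Synopsis, 11.1, 11.2 and Table 2 | No blood ketone meter or strip |
| Protocol 2.1.10, study meter | Described as measuring capillary glucose; no ketone function stated |
| Protocol 14.1.6 | Meter ketone testing implied, with no matching device, instruction or record |

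**Step 3: is there a bridge?** No section says how a urine result is to be read against 0.6 mmol/L. The DKA definition in the same Section 14.4 is a useful contrast: it accepts ketones in either blood or urine, so urine data can serve it. The severe hyperglycemia definition contains no such alternative.

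**Step 4: other routes to a blood value.** Section 14.2 expects investigators to supply medical records supporting an adverse event, and Section 14.5 has them review treating-facility records where these exist. A blood ketone value found there would satisfy (a). A symptom-free episode handled at home may generate no such record.

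**Step 5: review.** Under Section 14.7 a severe hyperglycemia episode reaches the committee only if it is also an SAE, SADE or UADE, or is reported as DKA.

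**Step 6: direction and size.** Let s be the share of true events that qualify on ketones alone, and c the share of those for which outside records supply a blood value. With the definition applied literally:

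counted / true = 1 − s × (1 − c)

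This is below 1 whenever s > 0 and c < 1, so the bias is downward. The documents give neither s nor c. Purely to show how the formula behaves, assume 200 subjects and a true incidence of 10%, that is 200 × 0.10 = 20 events:

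| s (assumed) | c = 0 | c = 20% (assumed) |
|---|---|---|
| 25% | 20 × 0.75 = 15 | 20 × (1 − 0.25 × 0.8) = 16 |
| 50% | 20 × 0.50 = 10 | 20 × (1 − 0.50 × 0.8) = 12 |
| 75% | 20 × 0.25 = 5 | 20 × (1 − 0.75 × 0.8) = 8 |

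The counted fraction runs from 5/20 = 25% to 16/20 = 80%. That spread reflects only the assumed inputs and is not an estimate for this trial.

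**The case against.** The best case for the plan has five parts.

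1. *The supply list is not exhaustive.* Section 11.3 also omits meter strips and reservoirs, although both appear elsewhere in the protocol. Table 1 lists unspecified ketone strips separately from urine strips, and Section 14.1.6 implies finger-stick ketone testing. A reader might infer that the trial supplies urine tests and nothing else; the documents do not go that far. What they do show is that every test with a stated sample type is a urine test. Section 14.1.6, with nothing behind it, is one more inconsistency to resolve and does not close the gap.

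2. *Symptom-free events are not invisible.* A reader might infer that they cannot be counted at all. That is too strong. Outside medical records may hold a blood value. Daily urine results are entered in CareLink Clinical, and glycemic problems are to be reported as adverse events, so an episode may appear in the general summary. What is missing is a rule that turns those records into a severe hyperglycemia event.

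3. *The committee sees serious cases.* This is correct for episodes that are also an SAE, SADE or UADE. It does not help with non-serious, symptom-free episodes.

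4. *The outcome is descriptive.* Sections 6.4 and 3.1.6 plan no formal safety test, and the confidence limits for event incidence name only DKA and severe hypoglycemia. This stands and limits the weight of the point.

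5. *The more serious ketotic harm is covered.* DKA accepts either sample type, is adjudicated and receives an upper confidence limit. This also stands.

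**Conclusion.** The definition and the specified data collection do not match. Followed as written, the protocol cannot identify symptom-free severe hyperglycemia from its explicitly specified tests and records, except where a blood ketone value happens to exist outside them. The reported incidence is therefore biased downward.

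The size is unknown. A reader might want to attach a percentage to the understatement, but any such figure would only restate an assumed share of ketone-only events and an assumed rate of outside capture; the documents support neither.

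The conclusion rests on two assumptions: that the definition is applied literally, and that the unspecified ketone strips are not blood strips. If sites use urine results instead, the problem becomes inconsistency between centers rather than a clear downward bias.

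The effect is confined to one descriptive safety incidence in a single-arm study. The DKA endpoint does not share the mismatch, and the primary A1C analysis is untouched. The point should be corrected, but it does not threaten the trial's main conclusion. Redacted SAP text has not been counted as missing.

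**What to change.** - Reconcile Protocol Sections 14.4, 10.1, 11.3 and 14.1.6 and Table 1, so that the ketone criterion in the endpoint refers to the same measure that subjects are given and that is recorded. Correct the garbled ketone term in Section 14.4 at the same time. Which test and which cut-off to use is a clinical decision for the sponsor, and none is proposed here.
- In the safety tables under Protocol Section 6.4 and SAP Section 3.1.6, report severe hyperglycemia by the criterion that qualified it: ketone value or symptoms. The reader can then see how much each route contributes.

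The cost is a clarifying amendment and one table split. The case report form is not among the documents, so it cannot be said whether a new field is needed to record the qualifying criterion. The downside for the sponsor is that the reported incidence may rise.
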